1.7 Rationale

This proposal addresses a central challenge in cancer prevention and control - developing an effective intervention using a multidisciplinary team. Older adults with acute myeloid leukemia (AML) are at risk for worsening symptoms and functional decline during initial treatment. Symptom management and consistent monitoring are needed to identify symptom and functional needs early to improve symptoms and minimize functional decline.

This study will provide new findings in three important areas. First, we will test PACT, the first multi-disciplinary and integrated intervention designed to improve function for persons diagnosed with acute leukemia, who are at high risk for poor QOL, symptom burden, and functional decline. Second, because of limited access to specialty-trained palliative care providers, this intervention trains non-specialty providers in the disciplines of nursing, OT, and PT to provide palliative and supportive care, thus filling a gap in care. Third, we recognize that managing symptoms and function alone is not sufficient to achieve meaningful behavior change; by framing the intervention in the Adaptive Leadership Framework for Chronic Illness, we address the patients' adaptive challenges, such as emotional, motivational, attitudinal barriers, so that patients engage more fully in work required of self-management for reducing symptoms and functional decline.

2.0 STUDY PURPOSE AND DESIGN

This is a single institution, feasibility trial of 20 (10 control and 10 intervention) patients with the primary objective of assessing feasibility, acceptability, and change in pre and post measures of symptoms, function, and QOL by administering the PACT intervention.

Study subjects will be identified by the Study Coordinator through pre-screening through the electronic health record after being referred by the oncologists and pharmacists. Eligible patients will be approached by the Study Coordinator to confirm eligibility, which includes requesting permission of the patient's attending physician. Seven days prior to and within three days after initiation 1st cycle HMA or low-dose cytarabine + VENE, written informed consent will be obtained (A total of 10 days of recruitment period and baseline assessment).

First, ten participants in the control group will receive usual care. After the control patients have completed the study, then 10 intervention participants will receive the PACT intervention, a novel symptom management intervention, which aims to build patient skills to manage AML treatment-related, and chronic illness symptoms. Because patients receive chemotherapy during the first 7 days of hospitalization or clinic visit, the intervention will start at day 1 or day 2 of chemotherapy. During hospitalization, the PACT RN will assess AML symptoms daily (using PRO-CTCAE), and PACT OT and PT will assess function at baseline (day 1 or 2), days 3 or 4, and days 6 or 7. This study uses UNC hired staff of RNs, OTs, and PTs to deliver the intervention.

3.0 STUDY OBJECTIVES/ENDPOINTS

3.1 Primary Objective

Determine feasibility and acceptability of study methods and examine changes in pre- and post-treatment measures of function, patients' self-report of symptoms and QOL, and patients and caregivers' post self-report of readiness for discharge. We will include 10 control and 10 intervention patients.

Feasibility: We plan enrollment of 60% of those approached; achieve 75% retention rate, 75% of intended data collection; and no intervention-related adverse events. The PACT intervention team will have a reduced workload; we will record effort required to deliver the PACT intervention. These feasibility data will inform if, or to what extent, workload is affected to plan future studies and implementation. The team will receive 32 hours of training in palliative care and adaptive leadership approaches. Adherence will be monitored by electronic tracking from OT and PT notes and by self-report.

Acceptability: Assessed by interviews and surveys with patients and their caregivers about their experiences.

Changes in pre-and-post QOL, symptoms, and function: Compare changes between control and intervention.

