3.4 Primary Endpoint

3.4.1 Feasibility will be defined as: % approached, retention rate (% of consented patients who completed the intervention); % intended data collection, safety (# of adverse events).

3.4.2 Adherence will be monitored by electronic tracking from OT and PT notes and by self-report during the intervention.

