10.2 Sample Size and Accrual

Sample size for this study is mainly determined by time and resource (budget) constraints. We will allocate 26 patients to the two groups (12 per group). We assume 20% of values will be missing or otherwise unusable, yielding complete data for 10 patients per group for analyses. As stated

above, estimation rather than statistical inference is our focus, and so it is not this project's goal to have adequate statistical power. We can focus instead on precision, and for the primary outcome of QOL (standardized), the half-width of a two-sided 95% confidence interval would be .9SD, assuming 10 patients per randomized group. We obtained this result using nQuery Advisor v7.0 software.

We claim such a study as feasible if and only if both (a) recruitment rate (p) is high enough and (b) retention rate (q) is sufficiently high, i.e., if both p and q are large enough. More specifically, this is to test the following hypothesis:

$$H_0: p \leq 50\% \text{ or } q \leq 50\% \text{ vs } H_1: p \geq 80\% \text{ and } q \geq 70\%.$$

Denote N as the number of eligible patients we try to recruit, and Y as the number of patients who are recruited, X as the number of patients (among the Y who are enrolled) who complete the PACT intervention. The target value of Y is 20, and we assume (1) N follows a negative binomial distribution, $NB(20, p)$, (2) X , conditional on ($Y = 20$), follows a binomial distribution $B(20, q)$. We further assume that N and X are independent. We list cut-offs and associated type I error and power under different N and X values for rejecting the hypothesis of $p \leq 50\%$ and the hypothesis of $q \leq 50\%$.

Recruitment (N: total number of patients being approached)

Y	Rejection Area	Type I error ($p \leq 50\%$)	Power ($p \geq 0.80$)
20	$N \leq 20+12$	0.108	0.994
20	$N \leq 20+13$	0.148	0.997
20	$N \leq 20+14$	0.196	0.999
20	$N \leq 20+15$	0.250	0.999

Retention (X: total number of patients who complete the intervention)

Y	Rejection Area	Type I error ($q \leq 50\%$)	Power ($q \geq 0.70$)
20	$X > 8$	0.748	0.995
20	$X > 9$	0.588	0.983
20	$X > 10$	0.412	0.952
20	$X > 11$	0.252	0.887

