Under the independence assumption, the overall Type I error rate is the product of two individual type I errors, and the overall power is the product of power of two individual powers. We will reject the hypothesis of $p \leq 50\%$ if $N \leq 34$, and reject the hypothesis of $q \leq 50\%$ if $X > 11$. The resulted overall type I error is 4.9%, while the overall power is 88.6%.

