10.3 Data Analysis Plans

Feasibility Data Management and Analysis

Data will be collected on feasibility metrics. These include collecting and recording data on all patients approached for recruitment, along with an indicator of whether each patient is enrolled or not. The proportion of those enrolling, along with its 95% confidence interval, will be

computed. Of those enrolled, we will record whether there is attrition prior to each patient's end of follow-up, as well as the reasons for such attrition. The proportion of those retained, along with its 95% confidence interval, will be computed as 1 minus the proportion who experienced attrition from the study. The frequency of data values will also be tracked, and the proportion of non-missing data values, along with its 95% confidence interval, will be computed. The frequency and type of adverse events, including intervention-related adverse events, will be recorded. Staff hours reflecting the effort required to deliver the intervention to each patient enrolled into the intervention arm will be tracked; its mean and standard deviation will be computed across patients.

Acceptability Data Management and Analysis

Interviews will be transcribed by a professional transcription agency. Using Atlas.ti for analysis, Drs. [name] and [name] will read transcripts to derive codes. They will review and discuss labels to group codes into related categories and identify major themes through this process. After we define each major theme, we will identify corresponding exemplar quotes. We will address trustworthiness of analysis procedures and findings through creation of an audit trail to record data collection, coding, and analysis decisions. The interviewer ([name]) will make reflexive memos after each interview and review memos with corresponding audio recordings to discern linkages, gaps, and questions. When the two coders do not agree on their initial code, code negotiation and transcript review will occur.

Analysis of Change in Pre-and-Post QOL, Symptom, and Function

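### The feasibility rule in 10.2 has a type I error of up to about 25% under its own null, not 4.9%, and its retention count, read literally, can never reach the cut-off.

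*Combined protocol and SAP*

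**What the plan says.** **Decision rule (10.2).** "We claim such a study as feasible if and only if both (a) recruitment rate (p) is high enough", with retention (q) as the second condition. The null is p ≤ 50% *or* q ≤ 50%; the alternative is p ≥ 80% *and* q ≥ 70%. With Y = 20 enrolled, N (number approached) is negative binomial, X (number retained) is binomial, and the two are independent. The cut-offs are N ≤ 34 and X > 11. On the joint error the section states: "the overall Type I error rate is the product of two individual type I errors". It gives 4.9% type I error and 88.6% power.

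**Retention.** Section 10.2 defines X as those "among the Y who are enrolled) who complete the PACT intervention". Section 3.4.1 is similar, and lists further components: "retention rate (% of consented patients who completed the intervention); % intended data collection, safety (# of adverse events". Section 10.3 differs: the proportion retained "will be computed as 1 minus the proportion who experienced attrition from the study". Section 2.0 gives usual care to the first ten patients and PACT to the next ten.

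**Scope of feasibility.** Section 3.1: "We plan enrollment of 60% of those approached; achieve 75% retention rate, 75% of intended data collection; and no intervention-related adverse events". Section 10.1 mentions only recruitment and retention when it names feasibility. On data completeness, 10.3 says "the proportion of non-missing data values, along with its 95% confidence interval, will be computed"; it also records adverse events. It sets no pass mark for either.

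**The concern.** A null joined by *or* is true when either rate is inadequate, even if the other is excellent. The error that matters is therefore the largest chance of passing while at least one rate is at or below 50%. Multiplying the two component errors assumes that both rates sit at 50% together, which is the most favourable point on the boundary where either rate equals 50%. A reader relying on 4.9% would think a feasible verdict much stronger evidence than it is.

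The retention count raises a separate problem. If X means PACT completers among all 20 enrolled, the ten control patients can never contribute. The verdict then depends on whether the analyst follows 10.2 or 10.3.

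A smaller question is what the verdict covers. Sections 3.1 and 3.4.1 describe a wider notion of feasibility than 10.1 and 10.2, and the text does not say how the two relate.

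**Working it through.** **Inputs.** All from 10.2 unless noted: Y = 20; N ≤ 34; X > 11, that is X ≥ 12; null and alternative rates as above. Planned rates of 60% enrolment and 75% retention are from 3.1; ten PACT patients from 2.0.

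**Formulae.** N ≤ 34 means at least 20 enrolments among the first 34 approached, so P(N ≤ 34 | p) = P(Bin(34, p) ≥ 20). Retention passes with probability P(Bin(20, q) ≥ 12). By independence, P(pass) is the product.

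**Reproducing the plan's figures**

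| | Recruitment passes | Retention passes | Product |
|---|---|---|---|
| p = 50%, q = 50% | 0.1958 | 0.2517 | 0.049 |
| p = 80%, q = 70% | 0.9988 | 0.8867 | 0.886 |

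Both stated figures are confirmed at these points.

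**Error under the stated null**

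- p = 80%, q = 50%: 0.9988 × 0.2517 = 0.251.
- p = 50%, q = 70%: 0.1958 × 0.8867 = 0.174.
- Maximum: P(pass) rises with p and q, so it is approached on the edges of the null. With q = 50% and p near 1 it tends to 0.2517. With p = 50% and q near 1 it tends to 0.1958. The larger is 25.2%, about five times 4.9% (0.252 / 0.049 = 5.1).

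The maximum error is thus the larger of the two component errors, not their product.

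**Can X > 11 occur?** Only ten patients receive PACT, so literal completers are at most 10 of 20 (50%), and P(X ≥ 12) = 0. Under 10.3 all 20 can count as retained, and X can run from 0 to 20.

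**What holding 5% would take.** Each component error must then be at most 5%.

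- Recruitment: N ≤ 30 gives P(Bin(30, 0.5) ≥ 20) = 0.049, and N ≤ 31 already gives 0.075. Power at p = 80% with N ≤ 30 is 0.974.
- Retention: X ≥ 15 gives 0.021, and X ≥ 14 already gives 0.058. Power at q = 70% with X ≥ 15 is 0.416.
- Together: maximum error 4.9%, power 0.974 × 0.416 = 0.406.

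**Performance at the 3.1 rates.** P(N ≤ 34 | 60%) × P(X ≥ 12 | 75%) = 0.6274 × 0.9591 = 0.602. Recruitment accounts for nearly all of the loss: 0.627 against 0.999 at p = 80%. The recruitment cut-off, 20/34 = 58.8%, lies almost at the planned 60%.

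**Retention marks.** The cut-off is 12/20 = 60%; 75% of 20 is 15. A result of 12, 13 or 14 passes 10.2 but falls short of the plan, with probability 0.8867 − 0.4164 = 0.470 at q = 70% and 0.9591 − 0.6172 = 0.342 at q = 75%.

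**The case against.** **This is a pilot.** Section 10.2 says that estimation is the focus and that time and budget set the sample size. That stands, and it limits the harm: no sample size rests on the 4.9%. But the same section sets a yes-or-no rule with a stated error and power, and those figures should be right for the null it writes down.

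**The product is a valid calculation.** It is the maximum error for a null in which *both* rates are at most 50%. That is not the null stated, and it would not match a claim that needs both rates to be adequate.

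**The intended meaning of retention is easy to guess.** Probably so: the binomial with 20 trials and the attrition wording of 10.3 both suggest remaining in the study, in either arm. Still, 3.4.1 and 10.2 both refer to completing the intervention, so the text needs correcting.

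**Stronger readings a reader might infer.** One is that 10.2 wrongly drops data completeness and safety, so that a study with poor data or an intervention-related event would be called feasible in breach of its own endpoint. The documents do not establish this. Section 10.1 scopes feasibility to recruitment and retention, so the two-part rule may be deliberate, with the other components described under 10.3. Another is that a 60% cut-off contradicts the 75% in 3.1. It does not: 3.1 states what is planned, and a test cut-off normally lies below a planning target. A third is that the 88.6% is wrong because the rule passes only 60.2% of the time at the 3.1 rates. It is correct for its stated alternative, which 60% enrolment does not satisfy.

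**Conclusion.** Two faults in 10.2 are established.

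1. The type I error under the stated null is up to 25.2%, not 4.9%. This rests only on the plan's own model: Y = 20, negative binomial N, binomial X, independence.
2. X as worded cannot exceed 10, so the retention condition cannot be met; 10.3 uses a different definition. This rests on ten of 20 patients receiving PACT. Section 10.2 also mentions 26 patients at 12 per group. Even with 12 PACT patients, X > 11 would require every one of them to complete.

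The mismatch in scope between 3.1 and 3.4.1 on one side and 10.1 and 10.2 on the other is secondary. It is an unreconciled difference, not proof that either version is wrong. The gap between 60% and 75% retention needs a clarifying sentence only.

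**What to change.** **Type I error.** Either keep N ≤ 34 and X > 11 and restate the error as about 25%, leaving the 88.6% power in place; or choose new cut-offs and report the maximum error over the *or* null beside the power. The cost is a less favourable figure. Holding 5% with 20 patients would bring power to about 41%, as shown above, so openly accepting the higher error may be the more sensible course for a pilot.

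**Retention.** Use one definition covering both arms in 3.4.1, 10.2 and 10.3; the 10.3 attrition definition does this. State whether death, or removal under 9.4, counts as attrition, and settle whether Y is 20 or the larger number in 10.2. The 10.3 window runs to the end of follow-up and not only through the intervention (about 60 days), so observed retention may be lower.

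**Scope.** Before results are known, choose one: make data completeness and safety conditions for concluding feasibility, or state that 10.2 tests recruitment and retention only and that the others are reported descriptively against the 3.1 marks. The first lowers the chance of passing by an amount the documents do not allow one to compute. It also requires 3.1 (intervention-related events) and 3.4.1 (adverse events) to be reconciled. If the 60% and 75% in 3.1 are planning targets, say so, and report the 60.2% chance of passing at those rates, noting that recruitment drives it.

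All of this is wording and restated operating characteristics, with no added patients or data.

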10.0 STATISTICAL CONSIDERATIONS

10.1 Study Design

This is a pilot clinical trial of the PACT intervention in older adults with AML. The primary objective is to assess the feasibility (recruitment and retention) and acceptability of PACT intervention and examine change in pre and post measures of symptoms, function, and QOL comparing 10 control and 10 intervention patients with AML.

Qualitative research does not necessarily predict what might occur, but helps to understand in depth the characteristics of the situation and the meaning brought by participants and what is happening to them at that moment.

Interviews will be semi-structured, face to face with follow-up questions and probes to facilitate a deeper understanding of the patient, caregiver perceptions of the intervention. Interviews will take place on 4 oncology in patient's hospital room or private clinic room and will not last longer than one hour. An interview guide, developed in advance of data collection, will be used to provide a structure to the process (Appendix 13.1).

The interview prompts will focus on the overall perception of the PACT intervention. Each interview will be digitally audio-recorded. Brief field notes will be made before, during (in a non-discrete manner) and after the interviews to make note of points thought to be relevant at the time.

Pseudonyms will be used to protect the identity of the participants. The pseudonym will be linked to demographic and clinical information in a master log. The master log of study participants' names and study codes will be kept in a secure file cabinet in the investigator's locked office.

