13.1.1 For patient (control group)

Greeting

Thank you for being here today. We really appreciate you taking the time to participate in this discussion. My name is _____ and will lead the discussion today.

Role

My role today will be to ask some specific questions and to keep the conversation going. We have a lot to cover, so I may need to change the subject or move ahead with the discussion. However, please stop me if you want to add anything or if you have any questions. The interview today will last about 20-30 minutes.

Purpose

The main thing we are interested in today is hearing from you, the expert. We want to hear your experiences about being diagnosed with acute leukemia and the initiation of chemotherapy. Your experiences will help us gain valuable insight on challenges that patients with AML face during chemotherapy. This information will guide us to further develop interventions to manage these challenges in the acute leukemia population.

I would like to state that our conversation is being audiotaped to help us remember what is said. You may ask me to turn off the recorder at any time or simply say you do not want to answer a question. Everything said here today will be confidential. Nothing you say will be connected with your name.

Any questions before we begin?

This section will be conducted at discharge assessment of cycle 1 and cycle 2.

1. How would you describe your mobility before your diagnosis?
2. How would you describe your mobility before your diagnosis now?
3. What do you think will help you continue to stay active?
4. How would you describe your (physical/psychological) symptoms?
5. What has your experience been while being home?

Closing (5 minutes)

Is there anything else we have not yet discussed that you would like to mention related to what we've been talking about?

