13.1.2 For caregiver (control group)

Greeting

Thank you for being here today. We really appreciate you taking the time to participate in this discussion. My name is _____ and will lead the discussion today.

Role

My role today will be to ask some specific questions and to keep the conversation going. We have a lot to cover, so I may need to change the subject or move ahead with the discussion. However, please stop me if you want to add anything or if you have any questions. The interview today will last about 20-30 minutes.

Purpose

The main thing we are interested in today is hearing from you, the experts. We want to hear your experiences about noticing [patient's name] cognitive changes after being diagnosed with acute leukemia and receiving chemotherapy. These changes may include difficulties thinking and processing, concentrating, memorizing or any changes you notice may be related. Your experiences will help us gain valuable insight on challenges that patients with AL and caregivers face during chemotherapy. This information will guide us to have an in-depth understanding of cognitive impairment and to further develop intervention to manage these challenges in acute leukemia population and caregivers.

I would like to state that our conversation is being audiotaped to help us remember what is said. You may ask me to turn off the recorder at any time or simply say you do not want to answer a question. Everything said here today will be confidential. Nothing you say will be connected with your name.

Any questions before we begin?

This section will be conducted at discharge assessment of cycle 1 and cycle 2.

1. What would you have wished you had known about [patient's name] acute leukemia?
2. What else might we have done to be helpful to you during the [hospitalization/clinic visit]?

Closing (5 minutes)

Is there anything else we have not yet discussed that you would like to mention related to what we've been talking about?

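### Acceptability of study methods is part of the primary objective, yet neither group is asked about it directly, and sections 3.1 and 10.1 disagree on what is to be acceptable

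*Combined protocol and SAP*

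**What the plan says.** Section 3.1 (Primary Objective) opens with "Determine feasibility and acceptability of study methods", and the synopsis in 1.1 uses the same object. Section 3.1 then gives the means: "Acceptability: Assessed by interviews and surveys with patients and their caregivers about their experiences".

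Section 10.1 (Study Design) words the objective differently: "The primary objective is to assess the feasibility (recruitment and retention) and acceptability of PACT intervention". It adds that "The interview prompts will focus on the overall perception of the PACT intervention". Section 2.0 also links acceptability to delivery of PACT.

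On format, 10.1 says: "Interviews will be semi-structured, face to face with follow-up questions and probes to facilitate a deeper understanding". The rest of that sentence ties the understanding sought to perceptions of the intervention. The guides are in Appendix 13.1. The control-patient guide asks, for example, "How would you describe your (physical/psychological) symptoms", and the control-caregiver guide asks "What else might we have done to be helpful to you during the [hospitalization/clinic visit". Section 10.3 (Acceptability Data Management and Analysis) describes transcription, coding and themes, and no survey analysis. Section 3.4 lists feasibility and adherence endpoints, and none for acceptability.

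**The concern.** The study asks a good deal of patients outside PACT itself. Both groups answer 19 symptom items daily (5.3.2; about days 1 to 60 in Table 5). Both undergo the same functional battery (5.1). Section 1.4 describes a wrist device worn for up to 6 months. If acceptability of study methods is a primary aim, someone should ask patients about these procedures, and the control group is where they can be judged free of PACT.

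As written, the guides do not ask. The pilot is meant to inform a larger study (10.3 refers to the subsequent R01). Completion rates will show that data are missing. They will not show whether patients found a procedure acceptable, or why not. Under 2.0 the controls finish before PACT patients start, so an omission from the control interviews cannot be made good later.

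**Working it through.** The plan gives no figure for acceptability, so the check compares the passages and counts questions.

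**1. What is to be acceptable.**

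| Section | Object |
|---|---|
| 1.1, 3.1 | Study methods |
| 10.1 | PACT intervention |
| 3.4 | No acceptability endpoint |

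**2. Numbered questions in Appendix 13.1.**

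| Guide | Questions | Name survey, tests or wearable | Touch them indirectly | About PACT or its components |
|---|---|---|---|---|
| 13.1.1 control patient | 5 | 0 | 0 | 0 |
| 13.1.2 control caregiver | 2 | 0 | 0 | 0 |
| 13.1.3 intervention patient | 7 | 0 | 2 (Q2, Q3) | 5 (Q2, Q3, Q4, Q6, Q7) |
| 13.1.4 intervention caregiver | 5 | 0 | 0 | 3 (Q2, Q3, Q5) |
| Total | 5 + 2 + 7 + 5 = 19 | 0 | 2 | 5 + 3 = 8 |

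Intervention-patient Q2 concerns the nurse's daily conversation about symptoms. It bears on the daily survey because the PACT RN administers PRO-CTCAE in hospital (2.0). Q3 concerns the OT and PT visits, and those therapists carry out the tests. Neither question names the survey or a test, and no question in any guide mentions the wearable. The control guides (5 + 2 = 7 questions) cover mobility, staying active, symptoms, being home, information wished for, and help during the stay or visit.

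**3. Surveys.** No acceptability or satisfaction questionnaire appears in the 5.3 table, in Table 5, or among the 17 measures in 13.2 (13.2.1 to 13.2.17). The Care Transitions Measure asks about the discharge experience, but the plan assigns it to readiness for discharge. The survey part of the stated method therefore has no visible instrument, schedule or analysis.

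**4. When the interviews fall.** Control patients are interviewed at the discharge assessments of cycles 1 and 2. PACT patients are interviewed on days 6 or 7 of cycles 1 and 2, with further questions within 30 days of cycle 3. Cycle 2 treatment runs on days 31 to 37 (1.2), and Table 5 allows up to 7 days after the end of infusion. If the discharge assessment is that visit, the last control interview is no later than about day 37 + 7 = 44. With 30-day cycles, cycle 3 starts at about day 61, so 30 days after its start is about day 90. Both fall well short of a 6-month wear period, and the control interviews end before day 60 of daily reporting. Ratings at these interviews can cover experience to date only.

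**5. What ratings from 10 per group can show.** The exact 95% interval is about 44% to 97% for 8 of 10 favourable. For 10 of 10 the lower limit is 0.025^(1/10) = 0.69, giving 69% to 100%. Even unanimous approval would not exclude a true rate below 75%, the level 3.1 uses for retention and data collection. The ratings can therefore be described but cannot support a pass/fail rule.

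**The case against.** The strongest reply is that 10.1 defines the target as PACT. On that reading 8 of the 19 questions serve it, and controls, who never receive PACT, have nothing to rate. This stands as far as it goes: the intervention guides do address acceptability of the intervention. It does not remove the disagreement with 1.1 and 3.1. Even under 10.1, the surveys have no instrument and 3.4 has no acceptability endpoint.

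The second reply is that the interviews are semi-structured and allow probes. Three guides (13.1.1, 13.1.2, 13.1.4) close with an open question, and the control-caregiver question on what else might have helped invites feedback. Reasons for declining (5.1), reasons for attrition and the proportion of non-missing data (10.3) are also recorded, and nothing prevents tabulating completeness by instrument. All of this is real but indirect evidence. Section 10.1 directs prompts and probes to the intervention, and the closing question is limited to topics already discussed. Decliners have not experienced the procedures, and completeness is not opinion.

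A reader might infer that acceptability of study methods cannot be answered at all, or that controls supply no acceptability data. The documents do not support either. Intervention-patient Q2 and Q3, the probes, the open closings and the recorded reasons can all yield relevant material. What can be said is that the question is not put directly.

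Absence from 13.2 is not conclusive alone, because that list also omits the FACT-Leu subscale found in 5.3 and Table 5. Section 3.5 is redacted. But 5.3, Table 5 and 10.3 agree in showing no acceptability survey.

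**Conclusion.** The point holds as a gap in direct measurement and a conflict between sections. Acceptability of study methods is part of the primary objective in 1.1 and 3.1. No question out of 19 names the daily survey, the OT/PT tests or the wearable, 2 of 19 touch the first two indirectly, and 0 of 7 control questions concern a study procedure or ask about acceptability. The surveys named in 3.1 have no visible instrument or analysis. Section 10.1 sets a different object, which the intervention guides do serve.

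This rests on reading study methods as including the data-collection procedures put to patients, and on the redacted section 3.5 not holding an acceptability survey. It deserves correction because it affects a stated primary objective and the remedy is cheap, but it does not leave the objective without any evidence.

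**What to change.** 1. State one object of acceptability, worded alike in 1.1, 3.1 and 10.1: study methods, the PACT intervention, or both.
2. If study methods are kept, add the same brief rated items, each with an open question asking why, to both patient guides (13.1.1 and 13.1.3). They should cover the daily symptom survey, the OT/PT tests and the wearable to date. Use the interviews already scheduled, and compare groups at the cycle 1 and cycle 2 interviews that both have. The caregiver guides do not need these items, since caregivers do not undergo the procedures.
3. Put the items in place before control enrolment begins, because controls finish first.
4. Add one line to 3.4 naming the ratings, and one to 10.3 reporting them descriptively by group with exact 95% confidence intervals and no pass/fail cut-off.
5. These items then serve as the survey promised in 3.1. If they are not added, delete surveys from 3.1.
6. Before finalising the wearable item, reconcile 1.4, which describes the device, with 5.3 and Table 5, which do not list it.

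The cost is about two minutes per patient interview and an amendment to the guides, plus one line each in 3.4 and 10.3 and the wording changes above. No extra visit is needed.
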